9.3.2 Evaluation of Non-target Lesions

Because all intracranial lesions will be considered target lesions, this assessment is not applicable to this study.

9.3.3 Evaluation of Best Overall Response

The best overall response is the best response recorded from the start of the treatment until disease progression/recurrence (taking as reference for progressive disease the smallest measurements recorded since the treatment started). The patient's best response assignment will depend on the achievement of both measurement and confirmation criteria (see **section 9.3.1**).

Note: In some circumstances, it may be difficult to distinguish residual disease from normal tissue. When the evaluation of complete response depends on this determination, it is often recommended that the residual lesion be investigated (biopsy) before confirming the complete response status. Because this disease would require a brain biopsy in this situation, with potential increased risk to the patient, patients with an ambiguous complete response status will only undergo histological confirmation if deemed necessary for additional treatment interventions. If tumor is not the predominant feature of biopsy specimen, e.g., if only necrosis is present, or inflammation or gliosis are prominent, then progression will not be deemed to have occurred. [40]

9.3.4 Pseudoprogression

Pseudoprogression is a well-known entity in oncolytic viral therapy of glioma. Currently, the immunotherapy Response Assessment in Neuro-Oncology (iRANO) group is proposing criteria for determination of pseudoprogression in immunotherapy trials which are not yet published. [40] We will utilize the following criteria to address this phenomenon in this trial : If tumor appears to enlarge or demonstrates increased enhancement by MRI consistent with PD, patients will undergo repeat imaging and clinical assessments at 3 months to determine whether the changes demonstrate true progression or pseudoprogression. Note that the investigator may obtain an MRI prior to this 3 month interval as indicated. Should significant neurologic deterioration occur that cannot be ascribed to tumor or pseudoprogression related events such as seizures or medication changes (e.g., steroid tapers) the patient will be considered to have progressed. During the interval, the patient may be watched or treated with bevacizumab and/or dexamethasone at the discretion of the investigators. If the patient improves with bevacizumab (to be used

preferentially at a suggested dose of 10mg/kg IV, every two weeks, for three months; previous tumor progression on bevacizumab does not preclude its use herein) and/or additional steroid administration (to be used if bevacizumab is contraindicated or insufficient) and the MRI changes in lesion size/and or enhancement also improves, the patient will be determined to have not progressed but to have suffered pseudoprogression, and will continue follow-up within the trial under the previously defined schedule. Should neurologic symptoms and/or imaging changes progress despite steroid administration on follow-up imaging, the patient will be determined to have progressed and the date of progression shall be assigned to the date of the initial scan that demonstrated findings consistent with PD as defined above.

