529	Nervous system disorders	Central nervous system necrosis	Severe symptoms; medical intervention indicated	Accepted treatments for malignant glioma (for example radiation therapy) can produce CNS necrosis that requires medical intervention such as corticosteroid administration
531	Nervous system disorders	Cognitive disturbance	Severe cognitive disability; significant impairment of work/school/life performance	Both malignant glioma and its accepted therapies (for example radiation therapy) can produce impairment of work/school/life performance
532	Nervous system disorders	Concentration impairment	Severe impairment in attention or decreased level of concentration; limiting self care ADL	Both malignant glioma and its accepted therapies (for example radiation therapy) can produce impairment in attention or decreased level of concentration that affects self care ADL
536	Nervous system disorders	Dysesthesia	Severe sensory alteration; limiting self care ADL	Malignant glioma can produce alterations in sensory function limiting self care ADL
545	Nervous system disorders	Headache	Severe pain; limiting self care ADL	Malignant glioma can result in intracranial pressure resulting in severe headaches
567	Nervous system disorders	Pyramidal tract syndrome	Severe symptoms; limiting self care ADL	Malignant glioma can produce dysfunction of the pyramidal tract
571	Nervous system disorders	Seizure	Multiple seizures despite medical intervention	Malignant glioma can produce multiple seizures despite medical intervention
575	Nervous system disorders	Stroke	Severe neurologic deficit	Malignant glioma can produce stroke through its associated hypercoagulative state. Also, treatment for malignant glioma (for example bevacizumab, radiation) can result in stroke

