9.3.1 Evaluation of Target Lesions

“Response” is defined as follows:

Complete Response (CR) - Disappearance of all treated enhancing tumor on MRI scan, off steroids, and neurologically stable or improved.

Partial Response (PR) - greater than 50% reduction in the treated enhancing tumor on MRI scan, stable or reduced steroid dose, and neurologically stable or improved.

Progressive Disease (PD) - greater than 25 % increase in the treated enhancing tumor on MRI scan, stable or increased steroid dose, and neurologically stable or worse.

Stable Disease (SD) - all other situations

Some patients on this trial may be taking dexamethasone and/or bevacizumab. Those who have decreased the dose of one of these medications to one lower than that utilized at the time of the previous MRI AND this dose decrease has occurred within two weeks of the MRI shall not be determined to have progressed even if the MRI meets the criteria for PD above, but rather that MRI shall be considered non-evaluable for response. Similarly, should an increase in steroid dosage or bevacizumab dosage occur within two weeks of an MRI compared to the prior MRI, the patient will not be eligible for consideration of a CR or PR but instead that MRI will be considered non-evaluable.

Note that since this is considered an immunotherapy trial, the appearance of lesion(s) does not necessarily indicate PD.

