11.4 Analysis of Secondary Endpoints

11.4.1 Delineation of the local and systemic immune response to M032 administration.

- Virus reactivation and shedding will be detected by PCR and culture of serial serum and saliva samples.
- Immunogenicity of M032 will be evaluated by the use of ELISA to detect HSV antibody titers.
- Each of these binomial responses will be summarized by frequencies for each cohort and overall.

11.4.2 Gather preliminary information about the potential benefit of M032 in the treatment of patients with recurrent malignant gliomas.

- The percentage of patients experiencing complete response, partial response, stable disease and progressive disease will be reported by cohort and overall based on follow-up radiographic imaging.
- Changes in clinical disease status and steroid administration will be considered when reviewing changes in tumor volumetric size.
- All changes in tumor volume will also be analyzed with consideration of any other anti-tumor cancer therapies (either prior to M032 administration or following M032 failure) and the timeframes in which they were administered.

- Quality of life response: A Karnofsky Performance Status score will be recorded pre-treatment and then measured serially post-treatment for each patient. Time to KPS <60 will be measured for each patient by the Kaplan-Meier analytical method.

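### Improvement on bevacizumab or added steroids turns a PD scan into pseudoprogression with nothing to separate the two, so reported PFS, and less often response, can be biased in M032's favor

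*Combined protocol and SAP*

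**What the plan says.** All references are to the combined protocol and SAP.

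- **Trigger (9.3.1).** PD requires "greater than 25 % increase in the treated enhancing tumor on MRI scan", with conditions on steroid dose and neurological status.
- **Interval (9.3.4).** After such a scan, "patients will undergo repeat imaging and clinical assessments at 3 months"; an earlier MRI is optional. "During the interval, the patient may be watched or treated with bevacizumab and/or dexamethasone at the discretion of the investigators". Bevacizumab is to be used "preferentially at a suggested dose of 10mg/kg IV, every two weeks, for three months", and steroids if it is contraindicated or insufficient.
- **Ruling (9.3.4).** If the patient improves on this treatment and lesion size and/or enhancement also improves, "the patient will be determined to have not progressed but to have suffered pseudoprogression", and follow-up continues. If symptoms or imaging progress despite steroids, the event is dated back to the first PD scan.
- **Response (9.3, 9.3.1, 9.4.1).** Response is scored against the baseline MRI. CR and PR carry conditions on steroids and neurology but none on bevacizumab. A CR or PR must be confirmed at the next scheduled MRI.
- **Guard (9.3.1).** An MRI is non-evaluable for CR or PR "should an increase in steroid dosage or bevacizumab dosage occur within two weeks of an MRI compared to the prior MRI".
- **Analysis (9.5, 11.4.2).** PFS is a secondary endpoint with no event, censoring or sensitivity rule for added therapy. Section 11.4.2 takes other anti-tumor therapy into account for tumor volume only, and only when given "either prior to M032 administration or following M032 failure".

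**The concern.** The ruling uses improvement on an added drug as evidence that the tumor had not progressed. The protocol itself treats that drug as active. The stroke row of the Section 4.2 table says "treatment for malignant glioma (for example bevacizumab, radiation) can result in stroke". Exclusion 3.2.15 bars bevacizumab within 4 weeks of M032. Section 9.3.1 makes an MRI non-evaluable for CR or PR after a recent bevacizumab increase, and non-evaluable for PD after a recent decrease, so the plan accepts that the drug can change the scan. Improvement on bevacizumab or added steroids therefore cannot distinguish pseudoprogression from progression that responds to those drugs.

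Section 1.3 makes preliminary benefit, including PFS, the secondary objective. In the patients whose disease looked progressive, PFS as written describes M032 followed by bevacizumab and/or steroids, yet it is reported as PFS after M032. Because interval treatment is at the investigators' discretion, its use could differ between dose levels. Section 4.1.1 lets increased PFS or OS play a part in choosing the phase II dose if toxicity does not identify an MTD.

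**Working it through.** The plan gives no PFS median, target response rate or expected bevacizumab use, so there is no stated figure to reproduce. The check traces the rules and adds simple arithmetic, taking 3 months as 91 days.

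**1. Direction for PFS.** If progression is confirmed, the event is the first PD scan. If the patient is reclassified, the event falls later or does not occur. No branch gives an earlier date.

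**2. Size for one patient.** PD on Day 28 with improvement 3 months later: 28 + 91 = Day 119. PFS moves from about 1 month to at least about 4. The weight of one patient is 100/N: 100/24 = 4.2 points, 100/20 = 5.0, 100/8 = 12.5 (Section 4.1.2 gives 8 to 24 patients in total).

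**3. Reach of the two-week guard.** It acts only if bevacizumab was started or increased in the last 14 days before the MRI.

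| PD scan to next scan | Gap (days) | Start days outside the guard |
|---|---|---|
| PD scan to 3-month repeat | 91 | 91 − 14 = 77 |
| Day 28 to scheduled Month 3 | 91 − 28 = 63 | 63 − 14 = 49 |

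A prompt start at constant dose leaves the later scan eligible for CR or PR. The guard does not limit the pseudoprogression ruling at all.

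**4. Shrinkage needed for a PR.** With lesion size relative to baseline, PD at 1.25 × reference requires shrinkage of more than 1 − 0.5/(1.25 × reference). Section 9.3.3 takes the smallest post-treatment measurement as the reference for PD.

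| Reference (fraction of baseline) | Size at PD | Shrinkage needed |
|---|---|---|
| 1.0 | 1.25 | 60% |
| 0.8 | 1.00 | 50% |
| 0.6 | 0.75 | 33% |

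**5. Confirmation.** With PD on Day 28 and a prompt start, the suggested course ends near Day 119. A Month 3 response is confirmed at Month 6 (Day 182), about 63 days after the course. With PD at Month 3 the course ends near Month 6, and confirmation is at Month 9, about 91 days later. Confirmation often falls after the suggested course, but nothing requires it to.

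**6. Section 11.4.2.** A patient ruled not progressed has not failed M032, so interval bevacizumab lies outside the wording on prior and post-failure therapy.

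**7. Illustration only; every input is an assumption.** Let time to first PD be exponential with median m months. Let a fraction f of PDs be true progressions reclassified on the added drug, each postponed by g months. Then S(t) = 0.5^(t/m), and for g ≤ 6 the rise in 6-month PFS is f × [S(6 − g) − S(6)].

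| m | 6-month PFS by first PD date | Rise, f = 0.1, g = 3 | Rise, f = 0.5, g = 6 |
|---|---|---|---|
| 2 | 12.5% | 2.3 points | 43.8 points |
| 3 | 25.0% | 2.5 points | 37.5 points |
| 4 | 35.4% | 2.4 points | 32.3 points |

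The range, about 2 to 44 points, shows mainly that the documents do not pin the size down.

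**The case against.** Pseudoprogression has to be allowed for in an oncolytic-virus trial, and the rule is not lax in every respect. It requires clinical as well as MRI improvement, and it dates confirmed progression back to the first scan. Section 4.3 also allows bevacizumab as supportive care for symptoms of edema or raised intracranial pressure, so its use need not mean that the investigator believed the tumor had progressed. Section 11.1 lists concurrent medications, so its use would be visible. All of this stands. None of it supplies evidence that separates the two explanations for an individual patient, and a medication listing does not change how PFS is counted.

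The objection is stronger on response. A reader might infer that any shrinkage on bevacizumab becomes a PR. The documents do not support that. The lesion must fall more than 50% below baseline, which from 125% of baseline means shrinkage of more than 60%. Steroids must be stable or reduced, the patient must be neurologically stable or improved, and the next scheduled MRI must confirm it. A late start of bevacizumab would trigger the two-week guard. The response route is open but narrow.

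A reader might also infer that the bias reaches survival, dose finding or the phase II dose in general. It does not reach OS or the DLT-driven CRM, and Section 4.1.1 brings PFS into the dose choice only if no MTD is being reached.

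**Conclusion.** The point holds for PFS and, more narrowly, for response. Section 9.3.4 scores a PD scan as no progression on improvement that bevacizumab or added steroids could have produced, and no other rule in the plan catches this. For a true progression so reclassified, the error in PFS runs in M032's favor: about 3 months or more for that patient, and 4.2 to 12.5 points on a proportion for 24 down to 8 patients. An undeserved PR is possible but less likely. Steroids raise the same problem for PFS; for response, the CR and PR steroid conditions limit it.

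How many patients would be affected cannot be derived from the documents, and the illustrative range should not be read as an estimate. The rule will also correctly rescue some true pseudoprogressions, so PFS by the present rule is not shown to be wrong; it is the favorable bound. The guard calculation assumes that starting bevacizumab counts as an increase and that it starts soon after the PD scan.

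PFS and response are secondary and descriptive in a small, non-randomized phase 1 trial. This is a cheap improvement, not a flaw in the primary analysis.

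**What to change.** Change scoring and reporting only; leave treatment as it is.

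1. **Sections 9.5 and 11.4.2.** Keep PFS by the present rule and add a supplementary PFS. For patients reclassified after interval bevacizumab or added steroids, use the initial PD scan date as the event, except where histology or a repeat MRI taken before that treatment showed no progression. Present the two results as bounds. The histology exception fits Section 9.3.3, which already declines to call progression when tumor is not the main finding on biopsy.
2. **Sections 9.3.1 and 11.4.2.** Report separately any CR or PR first met after bevacizumab was started post-M032. Do not remove responses first met before it.
3. **Section 11.4.2.** Extend the wording on other therapy to treatment given during the pseudoprogression interval, with start and stop dates for each patient. The Section 8 calendar already has concurrent medications reviewed at every visit.

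The cost is some wording, one extra analysis and figures that may look less favorable. The supplementary version will count some true pseudoprogressions as events, because Section 9.3.4 requires neither histology nor a pre-treatment repeat scan. That is why it should be shown as a bound and not as a replacement.

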9.4 Confirmatory Measurement/Duration of Response

9.4.1 Confirmation

To be assigned a status of PR or CR, changes in tumor measurements must be confirmed by the next scheduled MRI after the criteria for response are first met. In the case of SD, follow-up measurements must have met the SD criteria at least once after study entry at a minimum interval of 12 weeks.

9.4.2 Duration of Overall Response

The duration of overall response is measured from the time measurement criteria are met for CR or PR (whichever is first recorded) until the first date that recurrent or progressive disease is objectively documented (taking as reference for progressive disease the smallest measurements recorded since the treatment started). The duration of overall CR is measured from the time measurement criteria are first met for CR until the first date that recurrent disease is objectively documented.

9.4.3 Duration of Stable Disease

Stable disease is measured from the start of the treatment until the criteria for progression are met, taking as reference the smallest measurements recorded since the treatment started.

9.5 Progression-Free Survival

Because this study is a non-randomized phase 1 trial that will enroll relatively few patients, progression-free survival will be reported as a secondary endpoint.

10. REGULATORY AND REPORTING REQUIREMENTS

Adverse events (AE) will use the descriptions and grading scales found in the revised NCI Common Toxicity Criteria for Adverse Events (CTCAE). This study will utilize the CTCAE version 4.0 for adverse event reporting. All appropriate treatment areas will have access to a copy of the CTCAE version 4.0. A table showing the expected adverse events associated with M032 and the related IMT terms can be found in **Appendix A**.

10.1 Adverse Event Reporting (AE; formerly known as Adverse Drug Reaction)

10.1.1 Adverse Event

An adverse event (AE) is defined as any untoward medical occurrence associated with the use of a drug in humans, whether or not considered drug related. An AE can be any unfavorable and unintended sign (e.g., abnormal laboratory finding), symptom, or disease temporally associated with the use of a drug, without any judgment about causality. An AE can arise from any use of the drug and from any route of administration, formulation, or dose, including an overdose.

An illness or condition present at study entry is considered a pre-existing condition and will not be considered an AE unless the pre-existing condition worsens during the course of the study. This change may be considered an AE. An AE that occurs after signing informed consent but prior to the administration of study drug will be considered not related to study treatment.

AE's that have a grade increase to 4 or 5 will be considered an SAE and reported as required.

All AE's, irrespective of relationship to study drug, which occur or worsen after signing of consent form until 30 days after administration of study drug, must be reported and documented on the AE Case

Report Form (CRF). All medications given for an AE will be reported on the Concomitant Medication CRF.

Hospitalizations that are expected due to the disease and those that are unrelated to the study drug or disease will be reported as AE’s unless it meets the requirements for a serious adverse event (SAE) which can be found in Section 10.1.2. Hospitalizations due to merely diagnostic reasons, examinations as a matter of routine or planned surgery and due to social indication do not represent a hospitalization in the sense of the term “serious”.

An AE is considered unexpected if it is not listed in **Section 5.1**.

10.1.2 Serious Adverse Event Expedited Reporting Guidelines – Phase 1 studies with investigational agents:

A serious adverse event (SAE) is defined as:

- Unexpected AE
 - For grade 1, no expedited reporting required
 - For grade 2, the investigator will be unbiased in assessing the relationship of the event and test article and discuss the possible relatedness to treatment with the Medical Monitor. If found to be possibly, probably or definitely related to study drug, an expedited report will be submitted within 7 working days.
 - For grade 3, the investigator will be unbiased in assessing the relationship of the event and test article and discuss the possible relatedness to treatment with the Medical Monitor. If found to be possibly, probably or definitely related to study drug, an expedited report will be submitted by phone within 24 hours with expedited report to follow within 7 working days.
 - For grade 4-5, regardless of relationship to study drug, a report will be submitted by phone within 24 hours with expedited report to follow within 7 working days.
- AE whose grade has increased to grade 3 or 4
- Adverse Event and IND safety reports will be filed in a timely manner with institutional authorities (IRB, IBC) as well as with the FDA and NIH/ORDA.
- All serious adverse events (Grade 3 or 4 toxicities) will be reported by fax, e-mail or phone within 24 hours and a written expedited report filed within seven days. Additionally, unexpected Grade 2 or Grade 3 toxicities will require a written expedited report within seven

days and Grade 3 unexpected adverse events will also require a fax, email, or phone call to the UAB IRB, the Neuro-Oncology CTMC, CCC PRC, FDA, and OBA within 24 hours.

- For events that are related, unexpected and serious, reporting will be reported to the FDA within 7 days of knowledge of the event.
- A list of agent-specific expected adverse events can be found in Appendix A.
- Any adverse event requiring an expedited report will also be reported immediately to the Medical Monitor and the investigator’s Institutional Review Board (IRB).

UNEXPECTED EVENT		EXPECTED EVENT	
GRADES 2 – 3 Attribution of Possible, Probable or Definite	GRADES 4 and 5 Regardless of Attribution	GRADES 1 - 3	GRADES 4 and 5 Regardless of Attribution
Grade 2 - Expedited report within 7 working days. Grade 3 - Report by phone to IDB within 24 hrs. Expedited report to follow within 7 working days.	Report by phone to IDB within 24 hrs. Expedited	Adverse Event Expedited	Report by phone to IDB within 24 hrs. Expedited report to follow within 7 working days.

(Grade 1 – Adverse Event Expedited Reporting NOT required.)	report to follow within 7 working days. This includes deaths within 30 days of the last dose of treatment with an investigational agent.	Reporting NOT required.	This includes deaths within 30 days of the last dose of treatment with an investigational agent.
---	---	-------------------------	--

